- 2) Overdose Risk Assessment: This assessment is used to determine the potential for future overdose based on prior overdose history, current drug use practices and social context for current drug use. This assessment is not standardized but is compiled from individual items of known risk factors for overdose.
- 3) World Health Organization Quality of Life (WHOQOL-BREF). This is a short assessment to measure general health and physical, social and emotional functioning.
- 4) World Health Organization Alcohol, Smoking and Substance Involvement Screening Test (WHO-ASSIST v.3). This is a multi-item tool to determine areas of substance use and misuse. This assessment battery screens for recent and lifetime use of a variety of substances, including illicit drugs, alcohol, pharmaceuticals and tobacco products.
- 5) Age of First Use: Subjects are asked to provide the ages they first used a variety of substances.
- 6) HIV Risk Assessment Battery: This assessment is used to determine the potential for contracting HIV, hepatitis and other blood-borne illnesses based on drug use and sexual use behaviors.
- 7) Overdose History: This assessment will collect information related to any prior overdose that the subject has experienced or witnessed.
- 8) EQ-5D-3L: This validated quality of life measure asks about problems in mobility, self-care, usual activities, pain and discomfort, anxiety and depression and overall health.

Locator information:

Subjects will be asked to provide a number of sources to ensure they can be contacted for 3, 6 and 12 month follow-up visits. However, because we anticipate a number of high risk subjects to be indigent, subjects may be enrolled if they provide at least one primary source of locator information.

Randomization

Subjects will be randomized to receive either standard of care or the study intervention. We will recruit equal numbers of subjects in the intervention and control arms of the study, meeting eligibility criteria as heroin user or primarily pharmaceutical opioid users.

Follow-up Visits

Follow-up visits will occur at 3, 6 and 12-month after enrollment. All interviews will be by phone. Most assessments given at the baseline interview will be repeated at each follow-up

point. In addition to the assessments subjects will be asked questions about whether they have naloxone and, if not, what happened to any naloxone that was given to them.

Secondary Data Sources

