The study was powered to address aim 1, the impact of the intervention on non-fatal overdose. For the study of each opioid user type (heroin and pharmaceutical opioids) the number of subjects needed in each arm of the study (intervention and comparison) to achieve power of 0.80 to detect a decline in the overdose rate from 20% to 10% at a confidence level of 0.05, is 219 subjects. To increase power somewhat and account for potential loss to follow up, we plan to enroll more subjects, 250 in each arm of each study, for a total of 500 heroin using subjects and 500 pharmaceutical opioid, non-heroin using subjects. Other outcomes to be analyzed include drug use and services utilization. Data on brief interventions in ED's shows declines in drug use and ED utilization of at least 40%. Specifically in Washington State, the Screening and Brief Intervention Referral and Treatment (SBIRT) found a 45% reduction in average days of drug use among high risk heroin users who received a brief intervention in an ED (from 15.8 days to 8.7 days in the prior month) and 41% reduction among high risk pharmaceutical opioid users (12.8 to 7.5 days).

Assumptions behind the power estimate are based upon an annual rate of non-fatal heroin overdose estimated to be a median of 25% across studies and for fatal overdoses approximately 1%. For the purposes of this sample size estimate we are conservatively assuming a total annual overdose rate for heroin users of 20%. We believe that a reduction of the OD rate by 50% may be possible based on the potential for additive effects of the OOPEN and the BBCC interventions. Preliminary data on overdose rates for pharmaceutical opioid

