Aim 1 Test whether the intervention group has lower rates of opioid overdose and longer time to occurrence of overdose. Overdose will be ascertained at 12 months via self-report and across at least 24 months via administrative data. Because randomized controlled studies are designed to account for potential confounding factors by distributing confounders, measured and unmeasured, equally across comparison and intervention groups, the initial unadjusted analysis will be a logistic regression analysis comparing the probability of opioid overdose in the two study arms. To examine differences in the time to overdose and to account for time varying covariates, such as overdose risk factors, survival analyses will be conducted with the outcome time to overdose(s). A Cox proportional hazards model will be used to investigate the possible association between these factors and event time. We will use sandwich standard error estimates in all statistical tests. Multivariable logistic regression analyses will be conducted to examine the association between predictors and moderators and of the odds of overdose occurrence. Predictors will include treatment assignment and overdose risk factors such as concomitant drug use, interruption in tolerance and homelessness. Potential effect modification will be assessed by including interaction terms for the treatment assignment by severity of opioid and other substance use as measured by the ASSIST. For the pharmaceutical opioid only group, effect modification by opioid user type will be assessed; opioid user typologies will be based upon which inclusion criteria subjects met.

Aim 2 Test whether the intervention group has fewer overdose risk behaviors. These are measured as both binary and continuous data. Binary data will be examined with logistic

regression and continuous data analyzed with ordinary least-squares regression. Analyses will adjust for the overdose risk behavior level or frequency reported at baseline as a concomitant variable, the outcome is the overdose risk behavior at 12 months, and the primary predictor is the treatment group assignment. We will compute robust standard error estimates for each model and use them in all hypothesis tests and confidence intervals.

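### The initial Aim 1 comparison leaves out baseline overdose history, although adjusting for it would bring a modest gain in power at little cost

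*Combined protocol and SAP*

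**What the plan says.** Under Planned analyses, Aim 1, the combined protocol and SAP says that "the initial unadjusted analysis will be a logistic regression analysis comparing the probability of opioid overdose in the two study arms". Its justification is that randomization spreads measured and unmeasured confounders evenly over the arms. Precision is not mentioned.

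The same paragraph plans two further kinds of model. One is a Cox model that allows for time-varying covariates. The other is a multivariable logistic model of predictors and moderators that includes treatment assignment. Its named risk factors (concomitant drug use, interrupted tolerance, homelessness) are given as examples. No Aim 1 model is designated as primary.

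Under Baseline Assessments, the Overdose History item is described thus: "This assessment will collect information related to any prior overdose that the subject has experienced or witnessed". The separate Overdose Risk Assessment serves to "determine the potential for future overdose based on prior overdose history", together with current drug use and its social context. The schedule table (Schedule of and Sources Data Obtainment) lists lifetime overdose history in its block of covariates and potential effect modifiers.

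Under Sample Size Calculation: "The study was powered to address aim 1, the impact of the intervention on non-fatal overdose". The requirement per arm, for each opioid user type, is given as "power of 0.80 to detect a decline in the overdose rate from 20% to 10% at a confidence level of 0.05, is 219 subjects".

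Elsewhere the plan does adjust. Aim 2 models include the baseline level of the behavior. The cost analysis controls for pre-randomization cost, expressly to lower variance and raise power.

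**The concern.** Balance under randomization makes an unadjusted comparison unbiased. It does not make it the most precise comparison available. When a covariate predicts the outcome, a logistic model that includes it has more power for the arm effect at the same sample size, and it accounts for any chance imbalance in that covariate. The plan uses this argument for costs, a secondary aim, but not for the aim that set the sample size.

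The covariate needs no new data collection, and the plan itself treats prior overdose as a marker of future risk. At stake is a small amount of power on the overdose outcome. There is also the question of which adjusted estimate will be reported. As written, the only adjusted logistic model could take in drug use or housing measured after randomization. Drug use and opioid use after interruption are themselves Aim 2 outcomes, so adjusting for follow-up values could absorb part of the treatment effect.

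**Working it through.** **Inputs from the documents.** Risks of 20% and 10%, power 0.80, alpha 0.05, 219 per arm and 250 enrolled per arm for each user type (Sample Size Calculation); 1:1 allocation (Randomization). Lifetime overdose prevalence is 25% in pharmaceutical opioid users and 49% in heroin users, taken from methadone entrants and not from this trial's population (Sample Size Calculation).

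**Assumed.** A two-sided test, since sidedness is not stated, and a yes/no prior-overdose covariate with an odds ratio of 2, 3 or 6 for later overdose. The documents give no value for this association.

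**1. The plan's own figure.** With a mean risk of 0.15:

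n = [1.960 × √(2 × 0.15 × 0.85) + 0.842 × √(0.16 + 0.09)]² / 0.10² = (0.990 + 0.421)² / 0.01 ≈ 199.

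With the continuity correction: (199/4) × [1 + √(1 + 4/(199 × 0.10))]² ≈ 219. The stated number is reproduced for an unadjusted, two-sided, continuity-corrected comparison.

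**2. Unadjusted logistic power.** The log odds ratio is ln(0.1/0.9) − ln(0.2/0.8) = −0.811, and SE = √[(1/0.16 + 1/0.09)/n] = √(17.36/n).
- n = 219: SE 0.2816, z = 2.880, power = Φ(2.880 − 1.960) = 82.1%.
- n = 250: SE 0.2635, z = 3.077, power = Φ(1.117) = 86.8%.

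**3. Adjusted logistic power.** The model is logit(risk) = a + b × prior overdose + t × arm. Here a and t are chosen so that the marginal risks stay at 20% and 10%. The SE of t comes from the inverse of the expected information, n × Σ w·p(1 − p)·vv′, summed over the four cells with v = (1, arm, prior overdose) and w the prevalence weight. Relative efficiency (RE) is the squared ratio of adjusted to unadjusted z.

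| Assumed OR | RE | Power, 219 per arm | Power, 250 per arm | Equivalent of 219 (219/RE) |
|---|---|---|---|---|
| unadjusted | 1 | 82.1% | 86.8% | 219 |
| 2 | 1.013–1.014 | 82.6–82.7% | 87.2–87.3% | 216 |
| 3 | 1.035–1.037 | 83.4–83.5% | 87.9–88.0% | 211–212 |
| 6 | 1.081–1.108 | 85.0–85.8% | 89.2–90.0% | 198–203 |

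Ranges cover prevalences of 25% and 49%. Example at OR 3, prevalence 25%, n = 219: 2.880 × √1.037 = 2.933, and Φ(2.933 − 1.960) = 83.5%.

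**4. Simulation check.** With sandwich standard errors, as the plan specifies, and 6,000 runs per scenario at 219 per arm, the gain was 1.1 points (OR 2, prevalence 49%), 1.3 to 1.4 (OR 3) and 2.8 to 3.2 (OR 5). With no association it was 0.02 points. The size is of the same order as in the table.

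**5. Change of target.** The marginal odds ratio is (0.1/0.9)/(0.2/0.8) = 0.444. The conditional odds ratio that gives the same marginal risks is about 0.44 at OR 2, 0.43 at OR 3 and 0.41 to 0.42 at OR 6. The adjusted model therefore estimates a slightly different quantity.

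**The case against.** The strongest reply is that nothing here is wrong. An unadjusted intention-to-treat comparison is valid under randomization, and it matches the calculation that gave 219. It also has at least the stated 80% power at that number. This stands. Enrolling 250 leaves room for 1 − 219/250 = 12.4% loss before the arm falls to 219. The plan states no loss rate, so a shortfall has to be assumed.

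A second reply is that the plan already allows for adjustment. Lifetime overdose history is listed as a covariate, and the multivariable model's list is open. This stands in part: overdose history could enter that model, but the plan does not commit to it.

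Some stronger readings are tempting, and the documents do not support them.
- A reader might infer that the unadjusted model is the main Aim 1 analysis. The text calls it initial and designates no primary model.
- A reader might infer that no planned logistic model adjusts for baseline prognosis alone. Covariate timing in that model is unspecified. Time-varying covariates are mentioned only for the survival analyses, and the named factors are also measured at baseline.
- A reader might infer that power is thrown away for no return. The loss is small, and the unadjusted model does give a marginal odds ratio, which plain logistic adjustment does not.
- Nothing in the documents ranks prior overdose above the other risk factors.

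**Conclusion.** The point holds as a modest improvement. The stated reason for not adjusting does not address precision, and the plan applies the opposite reasoning to costs. The gain is about 0.4 to 1.4 power points at an assumed odds ratio of 2 to 3, and up to about 4 points at 6, for 219 to 250 per arm. In subjects, at 219 per arm, this is about 3 to 8 per arm at an odds ratio of 2 to 3 and 16 to 21 at 6.

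These figures rest on the assumed association and on prevalences from a different population. A richer covariate, such as recency or number of overdoses, could predict better than the yes/no version used here. That baseline data precede randomization is inferred from the order of the sections and from the Intervention Description, which places baseline data before the intervention. The analysis as planned is valid and adequately powered on the plan's own assumptions.

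**What to change.** Specify the Aim 1 logistic comparison as a regression of overdose on arm and baseline overdose history. Define in advance how that history is coded (for example any versus none, or recency), and use pre-randomization values only. Report the standardized risk difference between arms with its confidence interval beside the conditional odds ratio, and keep the unadjusted comparison as supportive. State that the multivariable predictor and moderator model is exploratory, and say at what time its covariates are measured.

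The cost is SAP wording. No data collection or sample size changes. The one real drawback is that the adjusted odds ratio is conditional and differs slightly from the unadjusted one. The standardized risk difference gives readers a marginal effect.

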abusers (no regular heroin use) indicates a rate approximately half that of heroin users based upon analyses conducted by [name] of interviews from 1,661 clients entering methadone maintenance treatment which indicate a *lifetime* overdose rate for pharmaceutical opioid abusers (25%) that is half the rate of heroin abusers (49%). These findings were extrapolated to a 50% lower rate of *annual* overdose, the validity of which cannot currently be determined, but will be ascertained at the conclusion of this proposed study. We are assuming an annual overdose rate of 10% for pharmaceutical opioid users, or 20% over two years which is the amount of time over which follow up via administrative data will be collected. The power estimates above therefore address one year overdose rates for heroin and 2 years for pharmaceutical opioid users.

Planned methodology

Intent to treat analyses will be the primary analytic approach used to analyze the data resulting from this randomized controlled study. Intent to treat analyses compare those assigned to the intervention group to those in the standard care group, regardless of whether those in the standard care group receive some amount of the intervention.

Planned analyses

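### Aim 1 includes longer time to overdose, but the only survival model described adjusts for risk factors measured after randomization, so no total intention-to-treat comparison on time is specified

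*Combined protocol and SAP*

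**What the plan says.** Under Planned analyses, the aim reads: "Aim 1 Test whether the intervention group has lower rates of opioid overdose and longer time to occurrence of overdose". It therefore has two parts, whether overdose occurs and when.

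For the first part, "the initial unadjusted analysis will be a logistic regression analysis comparing the probability of opioid overdose in the two study arms". For the second, "To examine differences in the time to overdose and to account for time varying covariates, such as overdose risk factors, survival analyses will be conducted", followed by: "A Cox proportional hazards model will be used to investigate the possible association between these factors and event time". No log-rank test, arm-only Cox model or Cox model limited to baseline covariates appears anywhere.

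The neighboring models are more explicit. For the multivariable logistic model, "Predictors will include treatment assignment and overdose risk factors such as concomitant drug use, interruption in tolerance and homelessness". For Aim 2, "the primary predictor is the treatment group assignment" and "Analyses will adjust for the overdose risk behavior level or frequency reported at baseline as a concomitant variable".

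Planned methodology sets the general rule: "Intent to treat analyses will be the primary analytic approach used to analyze the data resulting from this randomized controlled study". The Objectives section words Aim 1 in terms of overdose rates only; the time component appears in Planned analyses.

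**The concern.** The time part of Aim 1 asks whether assignment to the intervention delays overdose. That is a question about the total effect of assignment, by whatever route it acts. A model that holds current risk behavior fixed asks something else: whether the arms differ in hazard among people with the same current behavior. If the counseling works by changing behavior, the second answer leaves out part of the first.

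As the plan stands, a reader could take the arm hazard ratio from the adjusted model as the intervention's effect on time to overdose, when some of that effect has been adjusted away. The choice of model for this part of a primary aim would also stay open until the data are in hand.

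**Working it through.** **Are the time-varying factors consequences of the intervention?** The Cox covariates are given only by example, so the set has to be pieced together.

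- Aim 1 names concomitant drug use, interruption in tolerance and homelessness as overdose risk factors, in the sentence on the multivariable logistic model.
- The Brief Behavioral Change Counseling section has the interventionist review mixing of drugs or alcohol with opiates, using alone, and using after abstinence, and then discuss changes.
- The schedule of measures lists drug and alcohol use frequency, opioid use after an interruption, and using without others present under Aim 2, with collection at follow-up.
- Housing is listed under covariates and potential effect modifiers, not under Aim 2.

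Many of the factors are thus post-randomization targets and outcomes of the intervention. Not all are.

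**The plan's own sample size.** Inputs from Sample Size Calculation: 20% versus 10%, level 0.05 (taken as two-sided), power 0.80.

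- Without continuity correction: n = [1.96 × √(2 × 0.15 × 0.85) + 0.842 × √(0.16 + 0.09)]² / 0.10² = 199.0 per arm.
- With correction: (199.0/4) × [1 + √(1 + 4/(199.0 × 0.10))]² = 218.5, so 219.

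The stated 219 is reproduced. It belongs to the yes/no endpoint and is not in dispute.

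**Can the planned sample support an arm-only test on time?** Proportional hazards is assumed.

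- HR = ln(0.90)/ln(0.80) = 0.1054/0.2231 = 0.472, so |ln HR| = 0.750.
- Events needed for power 0.80: 56 by Schoenfeld's formula, 62 by Freedman's.
- 250 per arm, no loss: 250 × (0.20 + 0.10) = 75 events. Power = Φ(0.750 × √75/2 − 1.96) = Φ(1.29) = 0.90.
- 219 per arm: 219 × 0.30 = 65.7 events. Power = Φ(0.750 × √65.7/2 − 1.96) = Φ(1.08) = 0.86.

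Yes, for each user type.

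**How large could the attenuation be?** No document input fixes this. As illustration only, with 75 events and an assumed share of the log hazard ratio removed:

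| Share removed (assumed) | HR | Power |
|---|---|---|
| 0% | 0.47 | 0.90 |
| 25% | 0.57 | 0.68 |
| 50% | 0.69 | 0.37 |

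The nearest figures in the plan are declines in days of drug use of 45% (15.8 to 8.7) and 41% (12.8 to 7.5) after a brief intervention. These are before-after changes, not differences between arms. If they are nevertheless treated as a between-arm fall d in the prevalence p of a factor that multiplies risk by R, the share is ln{[1 + p(1 − d)(R − 1)]/[1 + p(R − 1)]}/ln(0.472).

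- d = 0.41, R = 2, p = 0.3: share 13%, power 0.80.
- d = 0.45, R = 10, p = 0.7: share 66%, power 0.20.

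R and p are assumed, and the calculation takes the factor as perfectly measured; noisy self-report would make the attenuation smaller. The spread shows why no single figure can be given.

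**Covariates after month 12.** Interviews end at 12 months, but the pharmaceutical opioid comparison uses two years. At a constant hazard, events by month 12 are 250 × [(1 − √0.80) + (1 − √0.90)] = 250 × (0.1056 + 0.0513) = 39.2. That leaves 35.8 of 75 (48%) after the last interview. If interview-based covariates are used, the plan does not say what values apply then.

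**The case against.** The strongest reply is that the Cox sentence is loosely drafted and its intent is clear. The aim is about the intervention group, the survival analyses are meant to examine differences in time to overdose as well as to account for covariates, and intention to treat is the primary approach. That is persuasive. A reader might infer from the Cox sentence, which does not list arm, that the plan omits any arm comparison on time; the documents do not support that. But intention to treat settles who is compared, not which covariates enter. With arm read in, the model described still accounts for post-randomization risk factors.

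A second reply is that some covariates, such as homelessness, need not lie on the causal path, and that the set is never listed. This also stands, and it limits the claim: the hazard ratio could be attenuated, not that it must be.

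A third reply is that the consequence is narrow. The unadjusted logistic comparison comes first, the Objectives speak of rates, and the multivariable logistic model also mixes arm with risk factors without harm. This is correct for the yes/no outcome, where the adjusted model has an unadjusted arm test before it. The time outcome has no such counterpart, and that asymmetry is what remains.

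**Conclusion.** The point holds in a limited form. The time-to-overdose part of Aim 1 has no specified comparison that estimates the total effect of assignment. The one survival model described accounts for factors many of which the intervention is meant to change, so its arm hazard ratio should not be read as the intention-to-treat effect.

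Two stronger readings should be resisted. The primary overdose result is not compromised, because the powered yes/no comparison has its own unadjusted arm test. Nor can a loss of power be attributed to the plan: the attenuation figures above rest on assumed shares, risk ratios and prevalences.

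What the plan's figures do support is that an arm-only time test is feasible, with power of about 0.90 at 250 per arm without loss and about 0.86 at 219 per arm. Both assume proportional hazards and the planned 20% versus 10%. The omission is certain; its practical effect is not. It should be corrected before analysis.

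**What to change.** In Planned analyses, Aim 1, state that for each user type the time-to-overdose test is a log-rank or Cox comparison by randomized arm, either unadjusted or adjusted for named baseline covariates only.

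Keep the Cox model with time-varying risk factors, labeled as an exploratory risk-factor or mediation analysis. State that its arm coefficient, if fitted, is not interpreted as the intervention effect. List its covariates and say how follow-up after the 12-month interview is handled.

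The cost is a few sentences in the analysis plan. The arm-only test needs no new data or subjects, baseline risk assessments are already collected, and no planned analysis is lost.
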